[For the purposes of this protocol, 'investigator' refers to the Principal Investigator or their delegate].

STUDY SYNOPSIS

Protocol Ref. APM/18/1702001	Study drug: Atovaquone-proguanil (ATV-PG), Amodiaquine (AQ)
Title of the study: A randomized, double-blind, placebo controlled parallel group study in healthy adult subjects to determine the tolerability and safety of atovaquone-proguanil (ATV-PG) co-administered with amodiaquine (AQ)	
Principal Investigator: [name], MD FRCA FFPM	
Study centre: Richmond Pharmacology Ltd. Registered address: St George's University of London, [name] Clinical site: [name]	
Study Parts: N/A	Clinical phase: 1 (The study does not have therapeutic or prophylactic intent and does not plan to assess efficacy)
Objectives: Primary 
To assess the safety and tolerability of the approved curative dose of ATV-PG (once daily for 3 days) and the adult equivalent of the approved Seasonal Malaria Chemoprevention (SMC) dose of AQ (once daily for 3 days) when administered alone and in combination, in comparison with placebo. Secondary 
To determine the pharmacokinetics (PK) of atovaquone (ATV), proguanil (PG) and cycloguanil (CG), and amodiaquine (AQ) and desethyl-amodiaquine (DEAQ) following administration of ATV-PG and AQ alone and in combination.To determine the relationship between AQ and DEAQ and ECG parameters and to evaluate any impact of the combination with ATV-PG on this relationship.	
Endpoints: Primary 
Safety and tolerability as measured by the incidence of treatment-emergent adverse events (TEAEs) including the clinical signs, nausea, vomiting and diarrhoea, proportion of subjects with clinically relevant changes in laboratory safety tests (haematology, chemistry (in particular ALT, AST and bilirubin increases) and urinalysis), proportion of subjects with morphological and/or rhythm abnormalities on electrocardiogram (ECG), proportion of subjects with clinically significant changes in ECG time intervals (PR, QRS, QT and QTc intervals) and proportion of subjects with clinically significant changes in vital signs (systolic blood pressure, diastolic blood pressure and pulse rate). Secondary 
PK parameters derived by non-compartmental methods including maximum observed plasma concentration (C_{max}), time to maximum plasma concentration (t_{max}), area under the plasma concentration-time curve from time zero to last detectable plasma concentration (AUC_{0-t}), area under the plasma concentration-time curve from time zero extrapolated to infinite AUC_{0-inf}, terminal elimination rate constant (λ_z), terminal elimination half-life ($t_{1/2}$).Baseline corrected QTc (ΔQTc) as a function of the concentrations of AQ and DEAQ when administered alone, and when administered in combination with ATV-PG.	
Study Design: The study is a randomized, double-blind, placebo controlled, parallel group study to determine the tolerability and safety of ATV-PG + AQ, ATV-PG + AQ placebo, ATV-PG placebo + AQ, and ATV-PG placebo + AQ placebo administered once daily for 3 days to healthy adult male and female subjects.	

Fifty-two subjects will be enrolled and randomized to one of the four treatments in a ratio of 4:3:3:3 as described below:

- Treatment 1 (n=16) - ATV-PG 1000-400 mg + AQ 612 mg;
- Treatment 2 (n=12) - ATV-PG 1000-400 mg + AQ unmatched placebo;
- Treatment 3 (n=12) - ATV-PG unmatched placebo + AQ 612 mg;
- Treatment 4 (n=12) - ATV-PG unmatched placebo + AQ unmatched placebo.

Following the completion of dosing of the first 20 randomised subjects, Treatment 1 has been discontinued from further dosing in accordance with the Adverse Reaction (AR) rules in Section 4.4. Up to 24 further subjects will be included in the study, split in three cohorts of up to eight subjects.

The remaining three treatments will be re-randomised in such a way that across the whole study there will be still 12 subjects dosed with Treatment 2, 12 subjects with Treatment 3 and 12 Subjects with treatment 4. This is taking into account both the already dosed subjects with their originally randomised treatments and the newly randomised subjects yet to be included. Furthermore, within each cohort of up to eight subjects, each of the three treatments (2, 3, and 4) needs to be represented with a maximum of four and a minimum of one subject in the same cohort.

Subjects will be screened within 20 days prior to entering the study on Day -1. Each subject will receive verbal and written information followed by signing of the Informed Consent Form (ICF) prior to any screening procedures taking place. Subjects will be admitted to the study unit on Day -1 and will be discharged on Day 4.

All subjects will attend the unit for an outpatient visit on Days 8, 15, 22, 29 and a follow-up visit on Day 36 (+/- 1 day). All the assessments performed during the study are detailed in the study schedule of assessments (Table 1 and Table 2). Study design features as well as number of subjects may be adapted according to the Adaptive Features (Table 3). This study will use a sentinel dosing strategy, for full details see Section [3.3.4](#).

Number of subjects:

The planned total number of subjects for this study will be 52.

Main criteria for admission:

Black males or females, of sub-Saharan African origin (both parents are black and are of sub-Saharan African origin) will be included if they are aged between 18 and 45 years with a body mass index (BMI) between 18.0-25.0 kg/m². Subjects must agree to use effective methods of contraception.

Main exclusion criteria are: Current or recurrent disease (or condition) that could affect the action, absorption or disposition of ATV-PG or AQ, and any other significant disease or disorder which, in the opinion of the Investigator, may either put the subject at risk because of participation in the study, may influence the result of the study, or the subject's ability to participate in the study.

Anticipated test treatment(s) and mode of administration:

Oral doses of ATV-PG (1000-400 mg) and AQ (612 mg) administered once daily on Days 1 to 3 in the fed state (see Section [6.1.2](#) for details).

Reference treatment(s) and mode of administration:

Oral doses of unmatched placebo for ATV-PG and AQ.

Criteria for evaluation:

Safety analysis

Safety assessments will include standard laboratory safety tests (haematology, coagulation, biochemistry and urinalysis), vital signs (systolic blood pressure [SBP], diastolic blood pressure [DBP], Respiration rate, pulse rate and tympanic temperature), physical examinations, 12-lead ECG (RR, PR, QRS, QT, QTcF intervals and heart rate [HR]), continuous telemetry, and adverse event monitoring.

Pharmacokinetic analysis

The following pharmacokinetic parameters will be calculated from measured plasma concentrations of atovaquone (ATV), proguanil (PG), cyloguanil (CG), amodiaquine (AQ) and desethyl-amodiaquine (DEAQ): maximum plasma concentration (C_{max}), time to maximum plasma concentration (t_{max}), area under the plasma concentration-time curve from time zero to last detectable plasma concentration (AUC_{0-t}), area under the plasma concentration-time curve from time zero extrapolated to infinity (AUC_{0-inf}), terminal elimination rate constant (λ_z), terminal elimination half-life ($t_{1/2}$).

ECG analysis

Intensive cardiac assessments will be performed using food effects on the ECG to establish assay sensitivity. Analysis of drug related QT/QTc interval changes relative to plasma PK concentrations will be conducted. The ECG utilised for this analysis require adjudication by qualified cardiologists in accordance with principles set out in the ICH E14 guideline and subsequent Q&A documents. All ECG recordings are in triplicate and will be compliant with the correct recording and manual adjudication of ECG in thorough QT/QTc studies.

Statistical Methods:

Statistical analysis of safety parameters

Adverse events (AE), adverse events of special interest (AESIs), serious adverse events (SAEs), vital signs, ECG parameters, Profile of Mood States (POMs) questionnaire and clinical laboratory data will be listed and summarised using descriptive statistics. Basic Neurological Examination data will be listed only.

All AEs will be summarised and listed by using system organ class (SOC) and preferred term (PT) assigned to the event using Medical Dictionary for Regulatory Activities (MedDRA). Furthermore, these events will be summarised by the maximum intensity. The number of subjects who had drug-related AEs will also be summarised. Any AESI, SAEs and/ or AEs that led to withdrawal will be summarised and listed.

Statistical analyses of pharmacokinetic parameters

Non-compartmental analysis will be used for estimation of pharmacokinetic parameters.

For individual plasma concentration data, the actual time of ATV-PG and AQ administration and actual blood sampling time will be used in the derivation of the PK parameters. If there is any doubt in the actual time a sample was taken, then the scheduled time will be used.

AUC values will be calculated using the linear/log trapezoidal method, applying the linear trapezoidal rule up to C_{max} and the log trapezoidal rule for the remainder of the curve. Samples below limit of quantification (LOQ) prior to the first quantifiable concentration will be set to zero. Samples with concentrations below LOQ after the first quantifiable concentration will be set to 'missing' and omitted from the analysis. Other pharmacokinetic parameters will be calculated according to standard equations.

Statistical analyses of pharmacodynamic parameters

Two complementary sets of analyses will be performed: a per timepoint analysis and a concentration-QTc analysis.

For all quantitative ECG parameters, descriptive statistics will be given for the change from baseline. In addition, for QTc, a linear model will be fitted for each timepoint and the difference between each of the active treatments and placebo will be estimated based on this model and two-sided 90 % confidence intervals be given.

This analysis will be based on the change of QTc from baseline and will use baseline QTc and the concentrations of AQ, DEAQ and relevant analytes/metabolites (when AQ administered alone and in combination with ATV-PG) as covariates. Treatment and time will be used as discrete fixed effects. A series of linear models including one or more of the concentrations will be fitted and the most appropriate one will be selected based on the AIC (Akaike Information Criterion) and the size of the fixed treatment effect. A significant treatment effect (based on an F-test) will be considered an indication for model misfit. For the best fitting linear model, predictions of the effect on QTc will be made at the mean concentrations of the moieties involved at the t_{max} for each of these moieties.

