3. STUDY DESIGN

3.1 Overall study design

Study plan

The study is a randomized, double-blind, placebo controlled, parallel group study to determine the tolerability and safety of ATV-PG + AQ, ATV-PG + AQ placebo, ATV-PG placebo + AQ, and ATV-PG placebo + AQ placebo administered once daily for 3 days to healthy adult male and female subjects.

Fifty-two subjects will be enrolled and randomized to one of the four treatments in a ratio of 4:3:3:3 as described below:

- Treatment 1 (n=16) - ATV-PG 1000-400 mg + AQ 612 mg;
- Treatment 2 (n=12) - ATV-PG 1000-400 mg + AQ unmatched placebo;
- Treatment 3 (n=12) - ATV-PG unmatched placebo + AQ 612 mg;
- Treatment 4 (n=12) - ATV-PG unmatched placebo + AQ unmatched placebo.

Following the completion of dosing of the first 20 randomised subjects, Treatment 1 has been discontinued from further dosing in accordance with the Adverse Reaction (AR) rules in Section 4.4. Up to 24 further subjects will be included in the study, split in three cohorts of up to eight subjects.

The remaining three treatments will be re-randomised in such a way that across the whole study there will be still 12 subjects dosed with Treatment 2, 12 subjects with Treatment 3 and 12 Subjects with treatment 4. This is taking into account both the already dosed subjects with their originally randomised treatments and the newly randomised subjects yet to be included. Furthermore, within each cohort of up to eight subjects, each of the three treatments (2, 3, and 4) needs to be represented with a maximum of four and a minimum of one subject in the same cohort.

Subjects will be screened within 20 days prior to entering the study on Day -1. Each subject will receive verbal and written information followed by signing of the Informed Consent Form (ICF) prior to any screening procedures taking place. Subjects will be admitted to the study unit on Day -1 and will be discharged on Day 4.

All subjects will attend the unit for an outpatient visit on Days 8, 15, 22, 29 and a follow-up visit on Day 36 +/- 1 day (Figure 1). All the assessments performed during the study are detailed in the study schedule of assessments (Table 1 and Table 2). Study design features as well as number of subjects may be adapted according to the Adaptive Features (Table 3). This study will use a sentinel dosing strategy, for full details see Section [3.3.4](#).

[figure not shown]

Figure 1. Study flow chart.

Table 1. Schedule of assessments.

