3.3.7 Maximum Cohort Size

Following the reporting of an SAE in Cohort 1, it has been agreed between the SRC member to set the maximum cohort size at eight for all subsequent cohorts, with a minimum of one subject from each of the continuing treatment arms. A maximum of three subjects can be on the AQ + Malarone treatment arm within each cohort. This is to improve subject safety. Fewer subjects will ensure that all subjects can be assessed and managed (if required) properly, and everything can be documented properly.

Following the completion of dosing of the first 20 randomised subjects, Treatment 1 has been discontinued from further dosing in accordance with the Adverse Reaction (AR) rules in Section 4.4. Up to 24 further subjects will be included in the study, split in three cohorts of up to eight subjects.

The remaining three treatments will be re-randomised in such a way that across the whole study there will be still 12 subjects dosed with Treatment 2, 12 subjects with Treatment 3 and 12 Subjects with treatment 4. This is taking into account both the already dosed subjects with their originally randomised treatments and the newly randomised subjects yet to be included. Furthermore, within each cohort of up to eight subjects, each of the three treatments (2, 3, and

4) needs to be represented with a maximum of four and a minimum of one subject in the same cohort.

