3.1 Overall Design

Fifty-two subjects will be enrolled and randomized to one of the four treatment (Cohorts 1 to 4) in a ratio of 4:3:3:3 as described below:

- Treatment 1 (n=16) - ATV-PG 1000-400 mg + AQ 612 mg;
- Treatment 2 (n=12) - ATV-PG 1000-400 mg + AQ unmatched placebo;
- Treatment 3 (n=12) - ATV-PG unmatched placebo + AQ 612 mg;
- Treatment 4 (n=12) - ATV-PG unmatched placebo + AQ unmatched placebo.

Following the completion of dosing of the first 20 randomised subjects, Treatment 1 has been discontinued from further dosing in accordance with the Adverse Reaction rules of the protocol. Up to 24 further subjects will be included in the study, split in three cohorts of up to eight subjects.

The remaining three treatments will be re-randomised in such a way that across the whole study there will be still 12 subjects dosed with Treatment 2, 12 subjects with Treatment 3 and 12 Subjects with treatment 4. This is taking into account both the already dosed subjects with their originally randomised treatments and the newly randomised subjects yet to be included. Furthermore, within each cohort of up to eight subjects, each of the three treatments (2, 3, and 4) needs to be represented with a maximum of four and a minimum of one subject in the same cohort.

Due to randomization scheme with the initial 20 subjects, a total of 8 subjects have received treatment 1 before it was decided to terminate this arm.

Subjects will be screened within 20 days prior to entering the study on Day -1. Each subject will receive verbal and written information followed by signing of the Informed Consent Form (ICF) prior to any screening procedures taking place. Subjects will be admitted to the study unit on Day -1 and will be discharged on Day 4.

All subjects will attend the unit for an outpatient visit on Days 8, 15, 22, 29 and a follow-up visit on Day 36 +/- 1 day (Figure 1). All the assessments performed during the study are detailed in the study schedule of assessments. Study design features as well as number of subjects may be adapted according to the Adaptive Features. This study will use a sentinel dosing strategy.

[figure not shown]

Figure 1. Study flow chart.

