3.3 Sample Size

This is an exploratory study to evaluate tolerability and pharmacokinetics of each treatment group and is not based on formal statistical considerations. The numbers assigned to each treatment are deemed adequate to describe the tolerability, safety and pharmacokinetics.

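### The synopsis, Protocol 3.1 and 5.1, and SAP 3.1 still give 52 subjects with 16 on the combination, but the amended design can deliver up to 44 with 8 on it, replacements aside

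*Protocol*

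**What the plan says.** **Size as stated.** The synopsis, under Number of subjects: "The planned total number of subjects for this study will be 52". Protocol 3.1: "Fifty-two subjects will be enrolled and randomized to one of the four treatments in a ratio of 4:3:3:3 as described below", with 16, 12, 12 and 12 per arm. Protocol 5.1 gives the same split. SAP 3.1: "Fifty-two subjects will be enrolled and randomized to one of the four treatment (Cohorts 1 to 4) in a ratio of 4:3:3:3 as described below".

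**Size as amended.** The same sections go on to say that Treatment 1 (the combination) was stopped once the first 20 randomised subjects had been dosed. SAP 3.1 continues: "Up to 24 further subjects will be included in the study, split in three cohorts of up to eight subjects". Treatments 2, 3 and 4 are each to finish at 12. SAP 3.1 also reports that "a total of 8 subjects have received treatment 1". The protocol states neither 8 nor 44.

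**Where it is already handled.** Protocol 6.2.1 and SAP 3.4 present 16/12/12/12 as the allocation under the original protocol, then describe the amendment.

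**Justification.** Protocol 10.7 and SAP 3.3 say that the study is exploratory and has no formal sample-size basis. Both add: "The numbers assigned to each treatment are deemed adequate to describe the tolerability, safety and pharmacokinetics".

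**Limits on the combination.** Table 3 and Protocol 3.3.4 describe a sentinel group of 12 with 4 on Treatment 1. Protocol 3.3.7 caps cohorts after Cohort 1 at eight and adds: "A maximum of three subjects can be on the AQ + Malarone treatment arm within each cohort". The footnote to Table 6 says that the combination is not given from Cohort 3 onwards.

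**The concern.** The headline size is one that the amended design cannot reach, and it stands in current text, not in a change log. Someone who takes the planned size from the synopsis, or from the opening of SAP 3.1, will carry 52 and 16 into the study report.

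The shortfall is not spread over the arms. It falls entirely on the combination, which is the subject of the study title and rationale. The sentence calling the arm sizes adequate appears in a SAP that already knew the combination had 8 subjects, yet it says nothing about that arm having been halved.

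**Working it through.** **1. Reproduce the stated figure.** The ratio 4:3:3:3 has 13 parts. 52 × 4/13 = 16 and 52 × 3/13 = 12, and 16 + 12 + 12 + 12 = 52. The original plan is internally consistent.

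**2. Amended total, two routes.**
- By time: 20 already dosed + up to 24 further = up to 44.
- By arm: 8 (SAP 3.1) + 12 + 12 + 12 = 44.

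The 8 can also be derived from the other counts. Treatments 2 to 4 need 3 × 12 = 36 subjects and 24 are still to come, so 36 − 24 = 12 of the first 20 were on those arms. That leaves 20 − 12 = 8 on the combination.

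Shortfall: 52 − 44 = 8 subjects, or 8/52 = 15.4%. In the combination arm it is 16 − 8 = 8, so the whole shortfall sits there.

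**3. Can 52 still be reached?** The synopsis allows the number of subjects to change under Table 3. The only Table 3 feature that adds subjects is replacement of withdrawals (feature 2; see also Protocol 5.2), and no number is given. Replacements could lift enrolment above 44, but not in a stopped arm.

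**4. What halving the arm does to precision.** The documents give no event rate, so the 10% below is my assumption; 5% and 20% show the range.

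| Quantity | Formula | n=16 | n=8 |
|---|---|---|---|
| Upper bound, no events, one-sided 95% | 1 − 0.05^(1/n) | 17.1% | 31.2% |
| Upper bound, no events, two-sided 95% | 1 − 0.025^(1/n) | 20.6% | 36.9% |
| P(at least one event), true rate 5% | 1 − 0.95^n | 56.0% | 33.7% |
| P(at least one event), true rate 10% | 1 − 0.90^n | 81.5% | 57.0% |
| P(at least one event), true rate 20% | 1 − 0.80^n | 97.2% | 83.2% |

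The standard error of a combination-versus-placebo mean difference (12 on placebo, equal SD) is multiplied by √(1/8 + 1/12) / √(1/16 + 1/12) = 1.195, an increase of 19.5%.

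**5. The count of 8 against the protocol's limits.** The Table 6 footnote implies two cohorts before the arm stopped. Cohort 2 could hold at most 8. If the first 20 subjects were the 12-subject sentinel group plus one cohort of 8, the limits allow at most 4 + 3 = 7 on the combination, while the SAP reports 8. The 12 + 8 split is inferred; neither document states it. With 7, the other arms would need 36 − 13 = 23 further subjects and the total would be 7 + 36 = 43, so 44 remains the ceiling. The chance of seeing a 10% event would then be 1 − 0.9^7 = 52%.

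**The case against.** **The text largely corrects itself.** Amendment wording follows directly after most of the 52/16 statements, Protocol 6.2.1 and SAP 3.4 label the split properly, and SAP 3.1 itself reports the 8. This stands: a careful reader can derive 44. It does not rescue the Number of subjects line in the synopsis, which comes after the amendment text and carries no qualifier. It also leaves SAP 3.1 giving 16 and 8 for the same arm in one section.

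**No analysis depends on 52.** Correct. The safety set is every randomised subject who was dosed, and the safety summaries are descriptive by arm. A reader might infer that a power claim has failed or that the adequacy statement has been refuted. The documents do not support that: the study has no formal size basis, and the adequacy sentence names neither 16 nor 8. What can be said is that adequacy is asserted without comment on the arm that was halved.

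**Zero-event bounds suit this arm poorly.** Partly right. Protocol 4.4 reports extrapyramidal symptoms in a subject on the combination, so the bounds apply only to event types not observed. The arm is also smaller because a safety rule operated, and Protocol 1.1 foresees that the combination might not be well tolerated. Neither point makes 52 correct.

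**A limit was exceeded.** A reader might infer this from 8 against 4 + 3. The documents do not establish it. The size and make-up of Cohort 1 are not given, the word cohort is used loosely (SAP 3.1 attaches Cohorts 1 to 4 to the four-treatment scheme), and a replacement or a different Cohort 1 composition could explain the difference. The protocol's other counts also give 8.

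**Conclusion.** The stated total of 52, with 16 on the combination, cannot be delivered under the amended design. The current figure is up to 44 (8/12/12/12) plus any replacements: 15.4% fewer subjects overall and half the planned combination arm. This rests only on counts in the two documents.

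The consequence is lower precision for the combination, not an invalid analysis. For an unobserved event type the one-sided 95% bound is 31% rather than 17%. At an assumed 10% rate, the chance of seeing at least one event is 57% rather than 81%.

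The difference between 8 and 7 depends on the inferred 12 + 8 split and warrants a request to reconcile the passages, nothing stronger.

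**What to change.** 1. In the synopsis, Protocol 3.1 and 5.1, and SAP 3.1, give the current total as up to 44 plus any replacements (8/12/12/12). Keep 52 (16/12/12/12), labelled as the original plan in the manner of Protocol 6.2.1 and SAP 3.4, because the first 20 subjects were randomised under that scheme.
2. In Protocol 10.7 and SAP 3.3, say that the combination arm ended at half its planned size and give the precision that follows: the zero-event upper bounds and, with the 10% rate marked as an assumption, the chance of seeing at least one event.
3. State the size and arm composition of the cohorts that made up the first 20 subjects, and reconcile the SAP's 8 with the limits in Table 3 and Protocol 3.3.4 and 3.3.7. List a deviation under SAP 4.7 only if a limit was in fact exceeded. If the count changes, update items 1 and 2.

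The cost is wording only. No extra enrolment is needed, and dosing and analysis do not change. The one downside is that the stated size and precision become less favourable.
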